## **Phase 2: Treatment**

### **Titration Procedure**

1. Mask fit and mask evaluation.
2. Sleep technologist titrates the participant following AASM guidelines with his or her assigned mode to: eliminate all forms of abnormal SDB, consolidate sleep, and achieve REM sleep
3. MD will review study and determine starting pressures for each participant.
4. Study scored by an independent sleep technologist.
1. **Equipment Set-up Procedure at MSASVPAP** Adapt set to patient's assigned mode (CPAP or ASV) and prescribed pressure settings.
2. Participants given their device, tubing, and mask at the clinic within 2 days of their titration.
3. A research coordinator spends time teaching the individual how to properly use device and mask at home. Patient must be able to demonstrate mastery of mask and machine.
4. Possible side-effect symptoms (soreness on pressure points, red marks, aerophagia, etc.) discussed at this time to expedite care if an issue arises.

Once the patient is set-up, he or she receives instructions for follow-up steps and procedures. Scheduling of all Follow-up appointments and titration studies will take place at this time.

## **Phase 3: Follow-up**

### **Sleep Diary**

Once patients are set-up with their PAP device, they are expected to complete the online Sleep Diary each morning. It should take no longer than 5min to complete this brief survey. The sleep diary measures:

1. Subjective sleep indices:
  - a. Bed Time (BT)
  - b. Sleep Onset Latency (SOL)
  - c. Wake After Sleep Onset (WASO)
  - d. Total Sleep Time (TST)
  - e. Time in Bed (TIB)
  - f. Time Out of Bed (OOB)
2. Subjective sleep quality:
  - a. Sleep Quality rating: an 8-item Likert scale for sleep quality ratings in the morning
  - b. Global Morning Rating of Nightly Sleep: patients rate their sleep on a 0-100% scale.
3. PAP Adaptation:
  - a. PAP Units of Distress Scale (PUDS): a scale from 0-10 measuring current subjective distress as it relates to PAP therapy.

4. Patients will be prompted to indicate if something has changed, such as medications, when they fill out this daily diary

### **Follow-up Visits**

Participants will return every 2 weeks following their titration study for a follow-up clinic appointment conducted by sleep technologist with availability of [name] for relevant Q&A with patient. The following will be completed at each follow-up appointment:

1. Outcomes: Subject completes the following questionnaires:
  - a. Validated research instrument for tracking insomnia: ISI
  - b. Sleep related impairment: ESS, VAS-F, VAS-S, III, FSS, SDB-6
  - c. Quality of Life/Impairment: FOSQ-10, QLESQ, HSCL
  - d. PAP Therapy Tracking Tools: AEC, NOSE-8
  - e. Change Tracking Tool: PGA (Insomnia, Sleep Quality, Fatigue, Sleepiness, Energy level)
2. Data, download from the VPAP Adapt.
  - a. Usage
  - b. AHI, flattening %
3. Review device usage. Address concerns or questions including:
  - a. Progress and experiences with PAP
  - b. Benefits or lack thereof
4. Review sleep diary.
5. Determine if the subject has had any adverse events or adverse device effects.
  - a. Troubleshoot as needed

**Summary:** Following initial titration, the following steps will reoccur for the remainder of the protocol (refer to initial flow chart to see repetition of steps):

- Patients return on weeks 2 and 4 for Follow-up visits
- On week 6 they repeat titration process and complete Follow-up visit surveys and downloads
- Return on weeks 8 and 10 for follow-up appointments
- Return on week 12 for a final titration

### **Phase 4: Exit Interview**

The Exit Interview occurs 2-4 weeks after the final titration. The following will be completed during this visit:

1. Complete Follow-up Visits steps (Outcomes, Objective Data Download, review device usage and sleep diary, determine if there have been any adverse events)
2. Complete Exit Interview
3. Discuss next course of treatment such as:
  - a. Transfer to clinical care at our sleep center or another sleep center of their choosing

- b. Referral for alternative SDB treatment option
- c. Clarifying any intent for switching PAP mode from that used during the protocol
- d. Clarification of any insurance and DME questions going forward
- e. Formal transfer of PAP device into patient ownership
- f. Reimbursement of travel funds

### **Supplemental Follow-up Care**

Pressure intolerance, mask problems, leak, and other adaptation issues will be addressed to maximize PAP use in all participants. Follow-up visits, PAP Naps, and phone calls will be available to help subjects acclimate to PAP and troubleshoot barriers. Clinical judgment will be used to determine the type of follow-up the subjects will need over the course of the trial. Subjects will be followed until the PAP concern or issue resolves. The type of follow-up (titration or PAP Nap or phone call or clinic visit), the PAP area of concern, how the concern was addressed will be recorded in study documents and case report forms (CRFs).

1. PAP-NAP
  - a. Daytime abbreviated cardio respiratory desensitization study
    - i. Used for patients having difficulty adapting to any aspect of PAP
  - b. Individualized attention allows for gradual introduction to PAP with increased attention from a sleep technologist
  - c. Can also be used to address mask and intolerance issues.
  - d. Can occur at any time during the treatment, based solely on patient problems with compliance, and it often is an intervention that specifically can reduce drop-outs.
  - e. The number of PAP-NAPs per each patient will be limited to one. In special circumstances, a patient may need an extended PAP-NAP conducted at night.
2. Phone Consult
  - a. Participants have access to research assistants (and sleep technologists) to discuss or troubleshoot any issue that may come up during the course of the protocol, and as described on the Informed Consent Form, sleep technologists or [name] can be contacted during the overnight hours for urgent issues.
3. Clinic Follow-up
  - a. Follow-up to address any issues that need hands on attention (like mask issues) will be available to participants as needed.

### **Special Considerations**

Due to the nature of this study and its short duration, it is necessary to expedite care of any issues that may be barriers to rapid acclimation of PAP. Without reasonably rapid acclimation, results will be skewed toward less than optimal outcomes for either treatment arm, therefore the items below will be addressed both prophylactically and as they arise.

1. Mask Issues
  - a. Common mask issues discussed with the patient during Set-up as well as trouble shooting for each problem.

- i. Mouth breathing or mouth leak
  - chinstrap will be demonstrated
- ii. Mask leak
  - Proper mask fit
  - Tightening the mask
  - Chinstrap
  - Mask liners (mask liners will also be recommended for soreness, mask creases, and pressure spots)

2. Aerophagia (air swallowing)
  - a. PAP therapy complication that can be very uncomfortable or even painful.
  - b. We would like all participants to be aware of aerophagia and bring this symptom to our attention immediately.
  - c. Leg jerks, mask issues, reflux, NAR, and pressure intolerance can all cause aerophagia and will require clinical attention.
3. Leg Jerks (sub-cohort potential)
  - a. Patients who did not report restless leg or periodic limb movement symptoms on their intake, but had significant leg movements during their diagnostic PSG (not respiratory related) will be excluded from the study if the leg jerks persist on the titration.
  - b. Patients who do not report leg movement symptoms on their intake and do not exhibit leg movements on their diagnostic PSG but do exhibit leg jerks on any titration study, will require careful re-evaluation of clinical care by [name] to determine if leg jerks are a separate co-morbid medical issue requiring withdrawal from the study.

## **Research Rationale for Procedures**

### **Titration #1 (Initial)**

Participants return to MSAS sleep lab for a full night titration study during which only their assigned mode will be used. They will be fit with several masks and, with the help of a sleep technologist, will identify the best mask to start the PSG with and use during the study. The sleep technologist will titrate PAP pressure settings for each participant following AASM guidelines to eliminate all abnormal SDB wave forms, consolidate sleep, and achieve REM sleep with the assigned mode. All titrations will begin with low pressures, as recommended by the AASM, to help improve adaptation. Pressure settings will be determined to eliminate all SDB events (including RERAs). We anticipate that within the CPAP group the following trend will occur: aggressive treatment of RERAs will require increased pressure settings; these pressures will lead to expiratory pressure intolerance (EPI) or intolerance; and, “down” titration will be necessary for patient comfort. The highest pressures tolerated by the patient may not be equivalent to the pressures needed to effectively treat all SDB events. We would prefer to use pressures that treat all SDB events (including RERAs), but this may be an unrealistic goal for the CPAP group during the titration or the early adaptation period. Although we don’t anticipate as much of an issue of EPI or intolerance within the ASV group, we will follow the AASM procedure of “down” titration if it is needed. To avoid EPI and to help patients adapt to PAP, it may be

necessary to start CPAP patients on settings that do not treat all SDB events and increase settings over time. This approach may also occur with some ASV patients, but we expect the proportion of ASV patients with intolerance to be smaller than those using CPAP.

One other caveat to the above titration approach is the unlikelihood of finding the optimal pressures for any SDB patient upon first exposure to PAP therapy in the lab. Problems such as hysteresis, anxiety, psychophysiological discomfort, attention amplification, distress intolerance, and claustrophobia all weigh against an individual's ability to immediately adapt to PAP therapy. With this lack of immediate adaptation, certain pressure settings may prove intolerable. By way of an easier analogy, patients will be informed that learning to use PAP may be like learning to drive a car. In the beginning slower speeds (lower pressures) are more comfortable, and some training or experience may be needed before merging onto the highway to experience faster speeds (higher pressures). Returning to driving school (titrations in sleep lab) twice more during this protocol will enhance experience and expedite the capacity to adjust to higher pressures.

The studies will be scored by an independent sleep technologist to create consistency with baseline assessments and to prevent bias in the measurement of objective measures. Scoring technologist will be blinded to PAP mode. If discrepancy arises between independent scorer and MSAS technologist, the MD will review for final determination.

MD will review the study and prescribe PAP settings for each participant within 2 days of titration. It would be preferable to start all participants with their optimal pressure setting found during the titration, but as noted above lower pressures may be needed initially (preferably for no more than 1-2 weeks, leading up to first follow-up appointment) to help patients adapt to PAP therapy.

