##### **Second Encounter (in person, at sleep lab)**

1. Patients expressing interest in the protocol will be scheduled for and will complete the Diagnostic PSG.
  - a. [name] completes interpretation and recommendations per standard of care following a diagnostic study.
  - b. If OSA or UARS positive (and confirmed by independent scorer), patient is scheduled for full explanation of research project and signing of informed consent form.
  - c. If OSA or UARS negative, patient will be informed and will proceed with standard clinical care.

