##### **Third Encounter (in person, at sleep lab)**

1. PSG results discussion with research coordinator
2. Confirmation that the patient meets I/E criteria
3. Patient reviews and signs informed consent form
4. [name] conducts airway exam and answers patient questions.
5. Subject randomized to treatment arm
6. Completion of special baseline questionnaires
  - a. One week Sleep Diary (see below) with Global Morning Rating of Nightly Sleep
  - b. Insomnia Impairment Index

- c. Fatigue Severity Scale
- d. Intake Supplement

7. Schedule Titration #1

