#### Titration #3 (Final)

The final titration study will not only serve as an opportunity to reevaluate pressure needs but also to measure sleep indices: sleep onset latency, wake after sleep onset, sleep as proportion of TIB, sleep efficiency, sleep architecture, AHI, RDI, CAI, etc. This comparison will serve as the main pre and post objective comparison of data, because we anticipate the patient's adaptation to the device to be approaching an optimal point, and therefore, the objective metrics would most likely show the most well consolidated sleep compared to baseline. However, in some cases, pressure tweaks may still be needed, which then permits opportunity for another minor adjustment of the device. The patient then will be permitted to use these new settings for the next two to four weeks before the exit interview. This two to four week period then is quite important for that proportion of patients where pressure settings were still not optimal until undergoing the third titration. For some, if the minor pressure tweaks approach optimal, we will see noticeable therapeutic gains in that final few weeks of use on the new settings.

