#### **Polysomnography:**

Polysomnography will be completed at three different time points during the protocol: a diagnostic PSG study is completed during screening (not part of protocol) and three titration PSG studies are completed during the protocol (including a final study completed after four months of treatment with either CPAP or ASV).

PSGs will be conducted by registered sleep technologists at the investigative site. Titration protocols will be followed based on the subject's treatment arm. Scoring criteria will be applied using version 2.0 of the AASM Scoring Manual. PSGs will be scored by the sleep technologist on the night of the study as well as a third party sleep technologist who will be blinded to the treatment mode so as to preserve data integrity.

PSG parameters to be collected include:

- Total sleep time (minutes)
- Total recording time (minutes)
- Sleep efficiency (total sleep time/total recording time)
- Sleep stages (% and minutes of total sleep time): Stage 1, Stage 2, Stage 3, REM
- Awakenings index (arousals/hour)
- Arousal index (arousals/hour)
- Wake after sleep onset (minutes)
- REM consolidation index (total REM time in min/total # of discrete REM periods)
- Apnea-hypopnea index (events/hour)
- Obstructive apnea index (events/hour)
- Central apnea index (events/hour)
- Oxygen desaturation index (events/hour)
- Respiratory effort related arousal (RERA)
- Respiratory disturbance index (RDI)

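### Knowledge of the assigned mode can reach outcome data at two avoidable points: physician adjudication of disputed PSG scores, and a baseline diary week that follows randomisation

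*Combined protocol and SAP*

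**What the plan says.** **PSG scoring.** Under Titration #1 (Initial), the studies are scored by an independent technologist who does not know the PAP mode. The stated reasons are consistency with baseline and avoidance of bias. The section then adds: "If discrepancy arises between independent scorer and MSAS technologist, the MD will review for final determination". It continues: "MD will review the study and prescribe PAP settings for each participant within 2 days of titration". The on-site technologist runs a "full night titration study during which only their assigned mode will be used". The Polysomnography section has each PSG scored twice, by the technologist on duty and by a "third party sleep technologist who will be blinded to the treatment mode so as to preserve data integrity". Of the sleep indices measured at the last study, Titration #3 (Final) says: "This comparison will serve as the main pre and post objective comparison of data". At the diagnostic stage, the Second Encounter already uses the independent scorer: "If OSA or UARS positive (and confirmed by independent scorer), patient is scheduled for full explanation of research project".

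**Baseline diary.** Step 5 of the Third Encounter reads "Subject randomized to treatment arm". Step 6, after it, is the set of baseline questionnaires: a one-week sleep diary with the global morning rating, the Insomnia Impairment Index, the Fatigue Severity Scale and the Intake Supplement. The Informed Consent section also places randomisation directly after the consent signature. Primary Endpoint objectives lists the ISI, the diary sleep quality rating, the global morning rating, and change in diary SOL, WASO and SE.

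**The concern.** Blinded scoring protects an endpoint only if the blinded score is the one analysed. It matters most when the two scorers disagree, and that is where the plan passes the decision to someone who has to know the mode in order to prescribe settings for it. The PSG results are not peripheral: the hypothesis in the Background names objective sleep efficiency on PSG. The site has also recorded a directional expectation. On treating all events, including RERAs, it writes that "this may be an unrealistic goal for the CPAP group during the titration or the early adaptation period". Disputed events should not be settled with knowledge of mode in that setting.

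The diary baseline enters every change-from-baseline contrast for the diary variables. If a patient rates that week already knowing the arm, hope or disappointment about the device can move the baseline differently in the two arms. A group-by-time test cannot separate such a shift from a treatment effect. A patient who leaves during that week has been randomised but has no diary baseline.

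**Working it through.** The plan gives no figure to reproduce here. The check is of who knows the mode, who decides the score, and the order of the steps.

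**1. Who knows the mode**

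| Person | Knows the mode? | Source |
|---|---|---|
| Third-party scorer | No, stated | Titration #1 (Initial); Polysomnography |
| On-site technologist | Yes, titrates in the assigned mode | Titration Procedure; Titration #1 (Initial) |
| Physician | Inferred yes, prescribes settings for that mode | Titration Procedure; Titration #1 (Initial) |

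The only blinded party is the third-party scorer, and that scorer's result is not final when it is disputed. No section masks the physician for adjudication, defines a discrepancy, or says which score goes into the analysis. The physician may uphold the blinded score, but nothing requires it.

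**2. What the scoring rule can touch**
- PSG secondary variables in Secondary Endpoint Objectives: AHI, RDI, SE%, REM%, REM minutes = 5, all dependent on scoring.
- Studies, if the rule covers every titration and all 50 patients complete them: 3 × 50 = 150, of which 50 are Titration #3. This counts studies subject to the rule. The number actually disputed is unknown.

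**3. What the diary order can touch**
- Primary variables: ISI, sleep quality, global rating, SOL, WASO, SE = 6. From the diary: 5.
- Each patient lost in the diary week: 1/25 = 4% of an arm.
- ISI: a score of at least 15 is an inclusion criterion, so an ISI value exists before randomisation. The ISI is not among the step 6 questionnaires.
- Data Analysis applies a repeated measures ANOVA with a group-by-time interaction to the ISI and treats diary metrics in a similar way, so the diary baseline enters the comparison.

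**4. Illustration of sensitivity, on assumed inputs only**

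Suppose there is no true effect, but the baseline differs between arms by b SD because the arm is known. Let r be the correlation between baseline and follow-up. With two time points, the interaction test is a t test on change scores.
- SD of change = √(2(1 − r)).
- Standardised shift = b / √(2(1 − r)).
- Noncentrality = shift × √(25/2), with 48 degrees of freedom, two-sided 5%.

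Example: r = 0.5 and b = 0.2 give SD of change = 1, shift = 0.2, noncentrality = 0.2 × 3.54 = 0.71, and a rejection probability of 10.7%.

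| Assumed r | b = 0 | b = 0.1 | b = 0.2 | b = 0.3 |
|---|---|---|---|---|
| 0.3 | 5% | 6% | 9% | 14% |
| 0.5 | 5% | 6% | 11% | 18% |
| 0.7 | 5% | 7% | 15% | 27% |

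The documents give neither b nor r. The table shows how a shift of a given size would act; it is not evidence that one occurs.

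**The case against.** **Reach of the scoring rule.** The physician rule stands under Titration #1, just before the sentence on prescribing settings, so it can be read as a clinical decision about that study. The Polysomnography and Titration #3 sections contain no such override. This is a possible reading, but the rule directly follows the sentences on bias in objective measures and refers to the studies in the plural. Neither of the other two sections names a score of record. If care only was meant, one sentence would settle it.

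**The site's expectation about CPAP.** It is limited to the titration and early adaptation, and it concerns residual breathing events, not sleep staging. That limit stands. The expectation supports caution on AHI and RDI more than on SE% or REM, and more at Titration #1 than at Titration #3. The gap in the scoring rule does not depend on it.

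**Disclosure.** That patients know their arm during the diary week is an inference: no section says when assignment is disclosed. The step list is also not a strict clock, because a week-long diary cannot be finished in one visit, and the airway exam is placed differently in the Informed Consent section and the Third Encounter. The two flowcharts could not be read in the text available. All this is fair, but both readable descriptions put randomisation first, and none conceals the assignment from the patient.

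**No bias is demonstrated.** Both arms receive active PAP, and nothing shows that patients are led to prefer one at baseline. This stands; the concern is about exposure. It is also true that a patient who leaves in the diary week would have no post-treatment diary either, so the 4% count matters mainly for who is in the randomised set.

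**Conclusion.** The concern holds as stated. The plan's own rules let knowledge of mode reach outcome data at two points that could be closed. Disputed scoring can affect the five PSG secondary variables, and the post-randomisation diary week can affect the baseline of five of the six listed primary variables. The size and direction of any bias cannot be derived from the documents. Two inferences carry the point: that the physician knows the mode because of the prescribing role, and that patients may learn their arm before or during the diary week.

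The ISI, which Data Analysis takes first, is not shown to be affected at baseline. The device-download outcomes are outside the scoring rule. This is a change that should be made because it is cheap; it is not a defect that undermines the ISI comparison. Confidence is medium.

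**What to change.** **Scoring.** In Titration #1 (Initial) and in Polysomnography, state: *For every PSG endpoint, at all titrations, the value analysed is the blinded third-party score. Where it differs from the on-site technologist's score, the physician's determination applies to clinical care only.* Name the independent score of the diagnostic PSG as the PSG baseline, so that both sides of the comparison come from the same source. The plan's stated aim of consistency with baseline points that way but does not say it. If correction of scorer error is wanted in the analysis data, a second scorer masked to mode could adjudicate instead.

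**Baseline.** In the Third Encounter, move randomisation after the baseline diary week and questionnaires, and allocate before Titration #1. Change the Informed Consent section to match, for example: *Participants are allocated to an arm after giving consent and completing the baseline diary week and questionnaires.* Check that the flowcharts agree.

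**Cost.** These are wording changes in four places, using a scorer and a diary that are already planned. Allocation comes about a week later and has to be recorded at a later contact, such as Titration #1. Some patients may leave before randomisation and need replacing. Under the main scoring option, scoring differences stay in the analysis data as the blinded scorer left them. The physician's authority over care is unchanged.
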